9.5.3 Safety analysis

The safety analysis will be performed using the Safety Analysis Set, which will assess treatment-emergent adverse events (TEAEs). Detailed recordings of all severe adverse events and TEAEs leading to discontinuation from the study will be included. Changes in clinical laboratory parameters and vital signs at each scheduled time point from baseline will be summarized according to treatment groups.

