6.1 Schedule of Evaluations

Assessment	Enrollment: Day1	Run-in period (Day2-8)	Week 4 (Day 33- 39)	Week 8 (Day 61-67)
Informed Consent Form	\checkmark			

Efficacy and Safety of High-Dose Vitamin D Supplementation for Overactive Bladder Dry in Children: A Randomized Clinical Trial (Edition Number:3)

Demographics	\checkmark			
Medical History	\checkmark		\checkmark	\checkmark
SU	\checkmark		\checkmark	\checkmark
Bladder Diary		\checkmark	\checkmark	\checkmark
Current Medications		\checkmark	\checkmark	\checkmark
measurements of biochemistry.	\checkmark			\checkmark
measurements of hematology,	\checkmark			\checkmark
measurements of urinalysis.	\checkmark			\checkmark
Adverse Events			\checkmark	\checkmark

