6.2.2.2 Baseline assessment

All participants will have a 7-day run-in period during which children are asked to carefully record their OAB-dry symptoms. The purpose of this run-in period is to establish a baseline for evaluating the effect of the intervention measures investigated.

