7. SAFETY ASSESSMENTS

This study includes clinical interventions, and the primary focus of safety evaluation will be on assessing the adverse effects and exacerbation of clinical symptoms after oral administration of the drug. Patients will be encouraged to report any related complications or adverse events directly to us.

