7.1 Specification of Safety Parameters

Participants were required to take solifenacin and high-dose VDS as part of the study. Anticholinergic side effects, including dry mouth, blurred vision, constipation, and nausea, among others, may occur due to solifenacin use. If any of these symptoms occur, the medication will be discontinued, and the participant will be removed from the study. Over-supplementation of vitamin D can lead to symptoms of vitamin D toxicity, including anorexia, nausea, diarrhea, constipation, irritability, and somnolence. Any occurrence of these adverse drug reactions or serum vitamin D levels exceeding 100 ng/mL will be evaluated as unsafe.

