7.2 Methods and Timing for Assessing, Recording, and Analyzing Safety Parameters

Enrolled participants will undergo follow-up visits every four weeks. These visits

will include a questionnaire and physical examination to assess any drug-related adverse effects, as well as a test of their serum vitamin D levels. In case any adverse effects arise, safety parameters will be promptly evaluated.

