7.4 Reporting Procedures

In the event of any adverse event, investigators will be notified within 24 hours.

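### Treatment-emergent adverse events are to be analysed, but the plan states no pre-treatment record of most of the symptoms concerned and no rule for telling old complaints from new ones

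*Combined protocol and SAP*

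**What the plan says.** Section 9.5.3 sets the safety endpoint: "The safety analysis will be performed using the Safety Analysis Set, which will assess treatment-emergent adverse events (TEAEs". Neither that section nor any other defines treatment-emergent. Section 9.5.3 plans change from baseline for laboratory parameters and vital signs only.

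In the schedule (6.1), the row "Adverse Events" is ticked at Week 4 (Day 33-39) and Week 8 (Day 61-67) and is blank at Day 1 and in the run-in. The row "Medical History" is ticked at Day 1, Week 4 and Week 8, with no stated content. On the run-in, 6.2.2.2 says: "All participants will have a 7-day run-in period during which children are asked to carefully record their OAB-dry symptoms".

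Section 7.2 describes the four-weekly follow-up visits, which "will include a questionnaire and physical examination to assess any drug-related adverse effects". No matching use before treatment is described. Events may also be reported between visits. Section 7 says "Patients will be encouraged to report any related complications or adverse events directly to us", and 7.4 says "In the event of any adverse event, investigators will be notified within 24 hours".

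Section 7.1 names the symptoms of interest. For vitamin D: "Over-supplementation of vitamin D can lead to symptoms of vitamin D toxicity, including anorexia, nausea, diarrhea, constipation, irritability, and somnolence". For solifenacin it names dry mouth, blurred vision, constipation and nausea.

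**The concern.** Whether an event is treatment-emergent depends on a comparison: the symptom must be new, or worse than it was before treatment. Laboratory values have a baseline and a comparison rule in this plan. Adverse symptoms have neither.

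Most of the listed symptoms are non-specific and can be present in a child for reasons unrelated to treatment. A child who was already irritable or off food before allocation, and still is at Week 4, can enter the table as a treatment-emergent case.

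Safety is Specific Aim 2 (9.1), and the expected result is a similar profile across arms. Background complaints counted equally in each arm would make the arms look more alike on the ratio scale, and so would favour that expectation. The pre-treatment state cannot be reliably reconstructed once treatment has begun.

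**Working it through.** **1. Timing.** The visit windows imply that treatment starts at the end of the run-in: Day 8 + 28 = Day 36 (window 33-39), and Day 8 + 56 = Day 64 (window 61-67). The first scheduled adverse-event record is therefore 25 to 31 days after Day 8 (33 - 8 and 39 - 8).

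**2. What is recorded before treatment, set against the 7.1 symptoms.**

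| Pre-treatment source | What it covers |
|---|---|
| Medical History, Day 1 (6.1) | Content not stated; taken before the run-in |
| Medical-record review and eligibility questionnaire (6.2.1) | Eligibility criteria |
| Chronic constipation exclusion (4.2) | Long-standing constipation |
| PLUTS, measured from enrollment (9.5.2; item 13 of the form) | Daily bowel movement |
| Bladder diary and current medications, run-in (6.1) | OAB-dry symptoms; drugs |
| Laboratory tests, Day 1 (6.1) | No symptoms |

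Constipation has partial cover. Dry mouth, blurred vision, nausea, anorexia, diarrhea, irritability and somnolence have no stated cover. No section tells the analyst to use any of these sources to classify an event.

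**3. Illustration of size.** The plan gives no symptom rates, so these are assumptions. Let t be the true risk of an emergent event in an arm. Let p be the proportion of children with a pre-existing complaint that persists and is wrongly counted, the same in each arm and independent of t.

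Observed risk = 1 - (1 - p)(1 - t). The observed difference is then (1 - p) times the true difference. The arm size is the plan's: 87/0.90 = 96.7, rounded up to 97, which matches 9.2.

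| p | Miscounted children per 97 | True 5% v 15%: observed | Difference | Ratio | True 5% v 20%: observed | Difference | Ratio |
|---|---|---|---|---|---|---|---|
| 0 | 0 | 5.0% v 15.0% | 0.100 | 3.00 | 5.0% v 20.0% | 0.150 | 4.00 |
| 2% | 1.9 | 6.9% v 16.7% | 0.098 | 2.42 | 6.9% v 21.6% | 0.147 | 3.13 |
| 5% | 4.9 | 9.8% v 19.3% | 0.095 | 1.97 | 9.8% v 24.0% | 0.142 | 2.46 |
| 10% | 9.7 | 14.5% v 23.5% | 0.090 | 1.62 | 14.5% v 28.0% | 0.135 | 1.93 |
| 20% | 19.4 | 24.0% v 32.0% | 0.080 | 1.33 | 24.0% v 36.0% | 0.120 | 1.50 |

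Worked line, p = 10%, 5% v 15%: 1 - 0.90 × 0.95 = 0.145; 1 - 0.90 × 0.85 = 0.235; 0.235 - 0.145 = 0.090; 0.235/0.145 = 1.62.

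If p is read as the prevalence of pre-existing complaints, each row is an upper bound, because it takes every complaint to persist and to be counted. If only a share k is miscounted, use kp: a 10% prevalence with one in five miscounted gives the 2% row.

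**4. Dependence on equal ascertainment.** If complaints were miscounted in a drug arm but not in SU alone, two arms that both have a true rate of 5% would show 14.5% v 5.0% at p = 10%. The direction toward 1 therefore holds only when the arms are asked and classified alike.

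**The case against.** Much of the case on the other side stands.

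- **A blank pre-treatment Adverse Events cell is not in itself a fault.** A treatment-emergent event cannot start before treatment. What is missing is a baseline symptom state, not an adverse-event entry.
- **The schedule is not exhaustive.** PLUTS, QoL, physical examination and vital signs have no row, yet other sections collect or use them. A missing row is weak evidence by itself. But 7.2 also ties the questionnaire to follow-up visits, so the two sections agree.
- **A reader might infer that Day 1 history is the only pre-treatment record.** It is not, as the first table shows. It could even serve as the comparator if its content and use were specified.
- **A reader might infer that nothing is recorded before Week 4, so that onset rests wholly on recall.** Direct reporting (7) and 24-hour notification (7.4) contradict that. They bring some event dates forward but do not supply the state before treatment.
- **A reader might infer that any old complaint triggers discontinuation or removal.** Sections 7.2 and 8 refer to drug-related effects (section 8 also to worsening OAB symptoms), and the removal sentence in 7.1 follows from solifenacin side effects. An old complaint would first have to be misattributed. Attribution reduces the problem, but the plan gives the clinician no baseline list to judge against.
- **Equal error in all three arms is not established.** The safety set (9.3.3) requires a dose of study drug, which read literally leaves out SU alone. The listed symptoms also differ by drug.

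**Conclusion.** The gap is real and modest: an undefined endpoint term, a symptom questionnaire described only on treatment, and pre-treatment records that as stated cover little beyond bowel habit. Pre-existing complaints can be counted as emergent. With equal ascertainment this inflates rates and pulls ratios toward 1. The risk difference moves much less, from 10 to 9 points at p = 10% in the 5% v 15% case.

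The true size is unknown, because every rate used is an assumption. At p = 2% the effect is small. The figures should not be read as a loss of power in a planned comparison: 9.5.3 plans recording and summaries, with no between-arm test and no margin for similarity. Nor do the documents show a bias in favour of one treatment. The primary outcome is not affected. This is an inexpensive improvement that should be made, because the missing information cannot be recovered later.

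**What to change.** 1. Give the 7.2 symptom questionnaire once to all three arms at the end of the run-in, before allocation, with the 7.1 symptoms for both drugs and a severity grade for each. Tick the run-in cell in 6.1, labelled as a baseline symptom record.
2. In 9.5.3, define a treatment-emergent adverse event as a symptom absent from that baseline record, or one present there and recorded as worse after treatment starts.
3. Use the same questions in every arm on treatment, and state in 9.3.3 whether SU alone is in the safety set, since that arm would show the background rate.
4. Reconcile the start of treatment. Section 8 places it eight weeks after enrollment, whereas the schedule implies the end of the run-in. The definition in item 2 needs one start date.

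The cost is one more use of an existing questionnaire, which the QR-code forms (10.1) could carry, a few minutes per family, and a short definition. Randomisation already follows the baseline assessment (6.2.2.3), so the order of procedures does not change. Defining the term against Day 1 history alone would cost less, but would leave the symptoms that history does not specify. No change to the discontinuation rules in 7.1 or section 8 is proposed.

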8. INTERVENTION DISCONTINUATION

If any drug-related adverse effects or worsening of OAB symptoms in children during the intervention period occur, intervention measures should be discontinued. Otherwise, the intervention measures will start eight weeks after enrollment and will continue until the final data collection. At this point, study participants can withdraw their participation from this study.

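### The only laboratory safety analysis named is change at scheduled time points, so results drawn because of an adverse effect, and children removed before Week 8, can be absent from the by-arm laboratory table

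*Combined protocol and SAP*

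**What the plan says.** Section 9.5.3 (Safety analysis) gives one sentence on laboratory data: "Changes in clinical laboratory parameters and vital signs at each scheduled time point from baseline will be summarized according to treatment groups". The same section keeps treatment-emergent adverse events (TEAEs), with detailed records of those that lead to discontinuation. Section 9.3.3 restricts safety analyses to measured values, so nothing is imputed, and adds a per-protocol sensitivity analysis.

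The section 6.1 schedule has a row for "measurements of biochemistry" and similar rows for hematology and urinalysis. Each row has two ticks, which read as Day 1 and Week 8. There is no column for early termination or unscheduled visits.

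Section 7.2 states "Enrolled participants will undergo follow-up visits every four weeks" and describes those visits as including a questionnaire and examination "as well as a test of their serum vitamin D levels". It then adds: "In case any adverse effects arise, safety parameters will be promptly evaluated".

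Two rules govern stopping. Section 7.1, on anticholinergic side effects of solifenacin: "If any of these symptoms occur, the medication will be discontinued, and the participant will be removed from the study". Section 8, for all arms: "If any drug-related adverse effects or worsening of OAB symptoms in children during the intervention period occur, intervention measures should be discontinued".

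**The concern.** Specific Aim 2 in section 9.1 is the safety profile of high-dose vitamin D plus urotherapy, and the trial expects it to be similar to that of the comparators. A laboratory table that rests on scheduled visits describes mainly the children who reached those visits. Children who stop because of a side effect are plausibly the ones most likely to have an abnormal result. If they have no Week 8 panel, or have one taken after the intervention ended, and if the panel drawn because of the event has no place in the analysis, the table could look cleaner than the experience of all treated children. That would lean toward the similarity the trial expects. The loss could also differ between arms, because the stopping rules are worded differently for the two drugs.

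**Working it through.** The plan states no figure on this point, so the check is mainly textual.

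**1. When are laboratory values scheduled?**
- Section 6.1: biochemistry, hematology and urinalysis at Day 1 and Week 8 (Days 61 to 67). Serum vitamin D has no row of its own.
- Section 7.2: serum vitamin D at the four-weekly visits, hence also at Week 4.
- Section 6.2.4: serum vitamin D and all three panels listed under regular follow-up, without restriction to Week 8.
- Result: these sections disagree. Under section 6.1 the three panels have one post-baseline point. Under the broad reading of section 6.2.4 they have two. Vital signs are in the section 9.5.3 summary but have no row in section 6.1.

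**2. What happens to a child who stops early?**
- Solifenacin side effects (section 7.1): drug stopped and child removed from the study. There is no Week 8 panel and, under section 9.3.3, no imputed one.
- Stop under section 8: the intervention ends, and removal from the study is not stated. If the child attends Week 8, the value is off treatment. For example, a child stopped at the Week 4 visit (Days 33 to 39) would be off treatment for between 61 − 39 = 22 and 67 − 33 = 34 days.
- Vitamin D reactions, or a serum level above 100 ng/mL (section 7.1): classed as unsafe. Whether follow-up continues is not stated.

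**3. Where do results drawn because of an event go?** Section 7.2 produces them. Section 9.5.3 names only scheduled time points, and no section names a worst-value, any-time or early-termination summary. The per-protocol sensitivity analysis narrows the population and does not bring early stoppers back.

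**4. Scale, by assumption only.** Section 9.2 gives 87 / (1 − 0.10) = 96.7, hence 97 per arm. The documents give no rate of stopping for side effects. At 5%, 10% and 20% of 97, about 5, 10 and 19 children (4.9, 9.7, 19.4) would be removed. Let r be the number removed, a the proportion of them with an abnormal value, and b = 2% the proportion among completers. Assume that the values of those removed do not enter the table.

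Rate in all treated = [r·a + (97 − r)·b] / 97. Rate visible at Week 8 = b = 2.0%.

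| r | a = 20% | a = 50% | a = 100% |
|---|---|---|---|
| 5 | 2.9% | 4.5% | 7.1% |
| 10 | 3.9% | 6.9% | 12.1% |
| 19 | 5.5% | 11.4% | 21.2% |

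For r = 10 and a = 20%: (2.0 + 1.74) / 97 = 3.9%, so about 2 of 3.7 expected cases are unseen. If a equals b, nothing is distorted. The effect depends on abnormal results being concentrated in those who stop.

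**The case against.** The case on the other side has four parts, and much of it stands.

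First, a reader might infer that no laboratory value exists between baseline and Week 8. The documents do not support that. Serum vitamin D, the only laboratory parameter with a stated safety threshold (100 ng/mL), is tested every four weeks under section 7.2, and section 6.2.4 may place the other panels at Week 4 too. Even so, a child removed before Week 4 would have no scheduled panel, and results drawn because of an event would still have no assigned summary.

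Second, section 9.5.3 does not say that unscheduled values are excluded. Their omission is inferred from the absence of any other planned summary. Nor do early stoppers vanish from the safety analysis: the Safety Set keeps every child with a dose and safety records, and TEAEs leading to discontinuation are recorded in detail. Those records preserve the event. They do not supply laboratory data compared by arm.

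Third, a reader might apply the loss to the vitamin D arm, for instance by supposing that 5 of 97 children (5.2%) have an abnormality, that all five stop, and that the table shows 0 of 92. The text does not support this example. Removal is explicit only for solifenacin side effects, so the vitamin D denominator could stay at 97 with some off-treatment values. The example also assumes that no completer has an abnormality.

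Fourth, a contrast with urotherapy alone is weak. Section 8 also stops the intervention for worsening symptoms, which can occur in that arm. Read literally, section 9.3.3 admits to the Safety Set only children who took study drug.

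**Conclusion.** The concern holds in a limited form. The plan gives no laboratory analysis for results drawn when an adverse effect arises, and it does not say how values from children who stop early are handled. Under the section 6.1 schedule, a child removed for solifenacin side effects contributes no post-baseline biochemistry, hematology or urinalysis to the planned table. A child stopped under section 8 may contribute only an off-treatment value that is not marked as such.

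The by-arm table could therefore understate abnormalities. The documents do not show that it will, or in which arm. The size cannot be derived, because no stopping rate, abnormality rate or link between the two is given. The table of assumed rates shows only that moderate assumptions, not just extreme ones, can nearly double the true rate relative to the visible one (3.9% against 2.0%). The conclusion rests on reading the two ticks in section 6.1 as Day 1 and Week 8, and on taking the analyses named in section 9.5.3 as complete.

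**What to change.** **Section 9.5.3.** Keep the scheduled summary and add beside it, by arm:
- for each laboratory parameter, the worst post-baseline value from scheduled and unscheduled results, including those drawn under section 7.2;
- the number of children with any out-of-range value at any time after baseline;
- a flag on values taken after the intervention was stopped;
- the number of children with data at each visit.

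State which children from the urotherapy-alone arm enter these tables, since the Safety Set is defined by taking study drug.

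**Reconciliation.** Sections 6.1, 6.2.4 and 7.2 should agree on when each laboratory test is done, and the schedule should show where vital signs are taken. Sections 7.1 and 8 should agree on whether children who stop remain in follow-up. Which rule applies is for the sponsor and investigators to settle. The added tables are useful under any of them.

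**Cost.** One further safety table and a few lines of text, using results the plan already collects. An extra panel at the time of stopping would be an added or moved procedure, and this change does not depend on it. The downside is small: values drawn for cause raise the observed abnormality rate, and more so in an arm with more unscheduled tests. The new table should therefore stand next to the scheduled summary and not replace it.

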10. DATA COLLECTION AND QUALITY ASSURANCE

10.1 Data Collection Forms

In our study, we intend to measure and compare different outcomes using various tools, such as questionnaires and rating scales. Participants will be required to answer questions or rate their symptoms or behaviors on a scale. To minimize bias and increase the validity of the results, clinicians and independent evaluators will be trained to administer the questionnaires and scales without knowing which treatment group each participant belongs to. We will take steps to ensure that our data is accurate and that we adhere to the protocol. In cases where children can report their symptoms well, we will consider both what the child and parent say equally, and discrepancies between the two reports will be investigated further.

We will utilize QR codes to enable participants to fill out self-report forms, which can be scanned by a smartphone or tablet and linked to a website. Program alerts will be used to remind participants to answer all questions and enter valid values. We will maintain confidentiality and compliance throughout the study, labeling data by subject number, visit number, and date of visit only in our database. Participants will be given a unique ID number that only we can link to their names. To ensure data security, we will encrypt and password protect all electronic data transfers. Hard copies of personal health information and consent forms, as well as study measures on paper, will be kept in locked drawers by another researcher.

The research team will conduct regular reviews to evaluate the quality and completeness of data collected during the study, including patient intake and retention progress, patient compliance with visits, evaluations, and treatments as per the protocol, any adverse events or safety concerns, and the accuracy and completeness of key data elements required to characterize patients. These reports will assist the research group in determining the effectiveness of data capture and processing methods to facilitate scientifically sound analyses.

10.2 Data Management

The biostatisticians will manage the study database, while the principal investigators ([name]) will oversee the researchers and data management staff to ensure the quality and execution of the study. [name], MD, will supervise the data management and quality. The collected data will include various assessments, such as screening data, clinician- and patient-rated assessments, fidelity, visit adherence, and safety data, as well as interrater reliability and certification data. Weekly reports will track enrollment, completion, attrition, subject progress, and critical assessments. Baseline characteristics, protocol adherence, and other issues will be monitored using additional reports as necessary.

Data will be collected directly by patients and study staff through a QR code, which links to a website. The data will be exported to a relational database in Microsoft software for systematic querying and checking. Paper-based data will be entered by 2 independent staff members to prevent errors or missing data and verified by another staff member at the end of the study.

Monthly reports will monitor enrollment, completion, attrition, subject progress, and critical assessments. Additional reports will monitor baseline characteristics, protocol adherence, and other issues. Data will be de-identified using subject number, visit number, and date of visit to comply with local privacy requirements. Electronic data will be encrypted and password-protected, with only ID numbers being used to identify subjects. De-identified data will be transmitted for data analysis. Consent forms and hard copy protected health information will be kept in locked cabinets in a secure office.

